4.4.4.4 Imputation of Date of Birth

For the purpose of any data presentation and calculations requiring date of birth, any partially collected date of birth, or date of birth collected according to quarterly periods, will be imputed according to the following rules.

For all subjects enrolled prior to protocol version 6.0 who did not enrol with the updated CRF page to collect quarterly date of birth, any partial date of birth with a non-missing month and year was imputed to the first of the month at data entry. Any partial date of birth with a non-missing year was imputed to 1st January at data entry. Therefore, date of birth will be used as collected in the analyses and data presentations.

For all subjects enrolled under protocol version 6.0 or above, or who enrolled prior to protocol version 6.0 but with the updated CRF page to collect quarterly date of birth, the collected quarterly date of birth will be imputed to the middle of each quarter as follows:

Collected date of birth = 01JANXXXX, imputed to 14FEBXXXX

Collected date of birth = 01APRXXXX, imputed to 16MAYXXXX

Collected date of birth = 01JULXXXX, imputed to 15AUGXXXX

Collected date of birth = 01OCTXXXX, imputed to 15NOVXXXX

where XXXX is the collected year of birth.

4.4.4.5 Imputation of Dates for Calculations or Classification

Note that where calculations or classification of data relies on the use of partial collected dates, imputation of the partial dates may be performed for the purposes of the derivation. Where this is the case, specific details are provided in the relevant sections of this SAP.

4.4.5 Adjustment for Multiple Comparisons

The p-value applicable to the final analysis of 4SC at 18 months in the target population will be $p \leq 0.025$ 1-sided. For final analysis of the key secondary efficacy endpoints at 18 months in the target population, adjustment for multiple comparisons will be applied as described below. For all other analyses (i.e. for different endpoints or timepoints in the target population, or analyses in the overall population), analysis will be considered supportive only. Therefore, nominal p-values will be presented and the significance level applicable will be $p \leq 0.025$ 1-sided.

In accordance with EMA (European Medicines Agency, 2002) and FDA guidelines (U.S. Food and Drug Administration, 2017), the assessment of multiple key secondary efficacy endpoints at 18 months in the target population at the final analysis will be accounted for using the Hochberg procedure (Hochberg, 1988).

The key secondary efficacy endpoints are given in [Section 4.2](#) (time to rise from the floor, 6MWT, muscle strength evaluated by knee extension, muscle strength evaluated by elbow flexion, physical function as measured by total NSAA score, physical function as measured by cumulative loss of function on the NSAA, VL MFF as assessed by MRS). Each of these endpoints will be analysed and the resulting 1-sided p-values will be ordered in descending order, from least to most significant. The highest p-value will then be compared with 0.025, the specified level of significance for the primary endpoint at the final analysis for this study, and if it is >0.025 , the subsequent p-value will be considered in relation to $0.025/2=0.0125$. As

soon as the i th endpoint has a corresponding p-value $< 0.025/i$, the treatment effects for that endpoint and all of the endpoints following it are considered to be significant. A table will be presented summarising the p-values and associated adjusted 2-sided CIs from each of the key secondary efficacy endpoints with significance indicated according to the above approach.

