#### ***13.7.2 Analysis of Key Secondary Efficacy Endpoints***

##### Analysis of Key Secondary Endpoints

Formal analyses of functional key secondary endpoints (i.e., cumulative loss of function in the NSAA, change in 6MWT, NSAA, time to rise from floor and muscle strength by knee extension and elbow flexion) and Vastus lateralis MFF will take place in the target population at 18 months and will be achieved using the same approach as described for the primary /endpoint. Possible need for log transformation of these variables will be assessed prior to unblinding by assessment of ANCOVA model residuals without a treatment effect term.

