### ***13.7.3 Analysis of Exploratory Efficacy Endpoints***

Exploratory efficacy endpoints will be supportive only and not subject to alpha control; therefore nominal p-values will be presented.

The mean change from baseline to 18 months will be compared between givinostat and placebo in the target population for:

- Time to walk/run 10 meters;
- Quality of life assessed by Paediatric Outcomes Data Collection Instrument (PODCI);
- %-predicted 6MWT;

These endpoints will be analyzed using methods in line with those described for the primary and key secondary endpoints.

The fraction of subjects achieving the following endpoints at 18 months will be compared between givinostat and placebo in the target population:

- Proportion of subjects with  $\geq 10\%$  worsening in 6MWT at end of study;
- Proportion of subjects who loose ambulation during the study.

These endpoints will be analysed using a logistic regression model with terms for randomised treatment, concomitant steroid use and age at baseline. The odds for each treatment group will be extracted along with the odds ratio, associated 95% confidence interval and p-value.

The following endpoints will be compared between givinostat and placebo in the target population using Cox proportional hazards modelling:

- Time to 10% persistent worsening in 6MWT (Baseline through end of study);
- Time to loss of standing (Baseline through end of study);

The model will include terms for randomised treatment, concomitant steroid use and age at baseline. The hazard ratio will be extracted, along with the associated 95% confidence interval and p-value.

Moreover, exploratory analyses will be done in the target population to explore whether the effects of givinostat versus placebo administered chronically may be related to the type of DMD mutation, LTBP4 and Osteopontin genotype or to the biomarkers.

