4.4.2 Modelling Methods

All efficacy analyses will be conducted in the target population. Formal analysis will be conducted as described in this Section for the following in the target population: the primary efficacy endpoint at 18 months, all key secondary efficacy endpoints at 18 months. All other analyses (i.e. for different endpoints or timepoints in the target population, sensitivity or supplementary analyses, or any efficacy analyses later added for the overall population) will be supportive only and will not be subject to alpha control. Therefore, nominal p-values will be presented.

The change from baseline to 18 months after treatment with givinostat or placebo for the continuous efficacy variables described in Sections 4.1, 4.2 and 4.3 will be analysed using an analysis of covariance (ANCOVA). Note that the ANCOVA analysis of muscle strength will be performed on the normalised muscle strength variable (measured in N/Kg) only. In addition, the ANCOVA analysis of NSAA will be performed on the total NSAA score only, ANCOVA analysis of PODCI scores will be performed

on the standardised scores only (for each subscale and the global function scale as completed by subject and parent), and ANCOVA analysis of MRI parameters will be performed for the fat fraction results only. In each instance, the dependent variable will be the outcome being modelled and terms for the corresponding baseline value and re-derived age at first dose (in years and months) will be included as independent covariates in the model, with randomised treatment group and concomitant steroid use (according to the 4 possible strata) included as independent classification factors. Where the dependent variable is not the muscle strength test, MRS VL MFF, PODCI score or MRI parameters, additional covariates will also be included in the model for the following baseline values (where not already included): 4SC, time to rise from floor, time to run/walk 10 metres, distance walked in 6 minutes (for the analysis of percent predicted 6MWT, this will be replaced with baseline percent predicted distance walked in 6 minutes).

Least squares means and associated 2-sided CIs will be estimated for givinostat and placebo. The treatment effect, being the difference in least squares means (givinostat-placebo), will be presented along with the associated 2-sided CI and p-value.

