The time to event variables (time to 10% persistent worsening in 6MWT, time to persistent loss of standing) will be analysed using Cox proportional hazards modelling, including baseline values for: 4SC, time to rise from floor, time to run/walk 10 metres, distance walked in 6 minutes and re-derived age at first dose (in years and months) as independent covariates and randomised treatment group and concomitant steroid

use as independent classification factors. The hazard ratio will be presented, together with its associated 2-sided CI and p-value.

Where adjustment of alpha is applied to any of the above analyses per the methods described in Section 4.4.5, the 2-sided CIs will be subject to the corresponding adjustment. Thus the adjusted 2-sided CIs will be as indicated in the following table:

Analysis Time Point	Endpoint	Applicable p-value (1-sided)	Applicable p-value (2-sided)	CI (2-sided)
Final analysis	4SC at 18 months in the target population	$p \leq 0.025$	$p \leq 0.05$	95%
Final analysis	Key secondary efficacy endpoints at 18 months in the target population	$p \leq 0.025/i$ (i = rank according to Hochberg procedure)	$p \leq 0.05/i$ (i = rank according to Hochberg procedure)	$100(1-0.05/i)\%$ (i = rank according to Hochberg procedure)
General	All other analysis (supportive only)	$p \leq 0.025$ (nominal p-values presented)	$p \leq 0.05$ (nominal p-values presented)	95%

For the final analysis of key secondary efficacy endpoints at 18 months in the target population, unadjusted 95% CIs will be presented in the individual analysis tables. However, the applicable adjusted CIs following the Hochberg procedure will be given in an overall summary of these endpoints per Section 4.4.5.

Further, as a reflection of the overall totality of evidence for a treatment effect on functional outcomes, the primary endpoint and the functional key secondary endpoints (as detailed in Section 4.2.1) will be subject to assessment by Hochberg. This is equivalent to considering the primary and functional key secondary endpoints as equally important facets of the disease such that an improvement in any one, or more than one, of these endpoints can be considered to reflect a clinically meaningful benefit to the patient.

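### The key secondary Hochberg family starts at the full one-sided 0.025 with no condition on 4SC, so the chance of a false formal claim is about 0.027 to 0.049 under the global null, depending on correlation

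*SAP*

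**What the plan says.** SAP 4.4.2 names the formal analyses as "the primary efficacy endpoint at 18 months, all key secondary efficacy endpoints at 18 months", in the target population. Everything else "will be supportive only and will not be subject to alpha control". Protocol 13.7.3 draws a similar line: "Exploratory efficacy endpoints will be supportive only and not subject to alpha control".

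SAP 4.4.5 gives 4SC one-sided 0.025. It then applies Hochberg to seven key secondaries: rise from floor, 6MWT, knee extension, elbow flexion, NSAA total, NSAA cumulative loss and VL MFF. The entry level is the full 0.025: "The highest p-value will then be compared with 0.025, the specified level of significance for the primary endpoint at the final analysis". The next level is 0.0125, and so on. No sentence refers to the 4SC result. Protocol 13.7.2 says only that the key secondary analysis "will be achieved using the same approach as described for the primary" endpoint, with no order, gate or alpha split. The four changes in SAP Addendum 1 do not touch 4.4.5.

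SAP 4.4.2 also describes a second, overlapping procedure: "the primary endpoint and the functional key secondary endpoints (as detailed in Section 4.2.1) will be subject to assessment by Hochberg". It is explained on the basis that "an improvement in any one, or more than one, of these endpoints can be considered to reflect a clinically meaningful benefit to the patient". It is given neither an alpha nor a formal or supportive status.

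For reporting, "the applicable adjusted CIs following the Hochberg procedure will be given in an overall summary of these endpoints". The table in 4.4.2 sets their level at 100(1 − 0.05/i)%, where i is the Hochberg rank.

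**The concern.** If 4SC and the key secondaries are both formal, the error that matters for the set of formal claims is the chance that any one of them is false. Two procedures, each run at 0.025 with neither conditional on the other, do not hold that chance at 0.025. As written, 4SC can fail and a secondary can still be declared significant within the alpha-controlled part of the plan. The second Hochberg offers another route to a benefit statement in the same situation.

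The 4SC test keeps its own 0.025, so the primary conclusion is not at stake. What is at stake is the standing of a secondary result reported as formal after a failed primary.

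**Working it through.** **Inputs.** 4SC level 0.025 one-sided; seven key secondaries; Hochberg levels 0.025/i (all SAP 4.4.5). The documents give no correlations between endpoints, so I assume a common correlation ρ among eight normal test statistics and show a range.

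**1. The plan's own figures.** 0.025/2 = 0.0125, as SAP 4.4.5 states. The documents give no overall error for 4SC plus the key secondaries, so there is none to reproduce.

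**2. Global null, one direction.** The quantity is P(4SC p ≤ 0.025, or Hochberg rejects at least one of seven). At ρ = 0, Hochberg on seven true nulls rejects with probability 0.0247, so the total is 1 − 0.975 × (1 − 0.0247) = 0.0491. The simple bound 1 − 0.975² = 0.0494 is slightly higher. Numerical integration gives:

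| ρ | Secondary family alone | Any false formal claim, as written | Excess over 0.025 | With a gate on 4SC |
|---|---|---|---|---|
| 0 | 0.0247 | 0.0491 | 0.0241 | 0.025 |
| 0.3 | 0.0230 | 0.0452 | 0.0202 | 0.025 |
| 0.5 | 0.0203 | 0.0402 | 0.0152 | 0.025 |
| 0.7 | 0.0162 | 0.0336 | 0.0086 | 0.025 |
| 0.9 | 0.0111 | 0.0266 | 0.0016 | 0.025 |

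The excess is the chance that 4SC misses and a secondary is falsely claimed. A simulation of 2,000,000 trials per correlation agrees to within 0.0002. As ρ approaches 1 the total tends to 0.025.

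**3. Both directions.** SAP 4.4.1 applies every test in either direction. Counted that way against 0.05, the total is 0.0965 at ρ = 0 and 0.0531 at ρ = 0.9.

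**4. Partial null: 4SC and VL MFF null, six functional endpoints with large effects.** VL MFF then has the largest p-value in its family and is tested at 0.025. At ρ = 0 the error is 1 − 0.975² = 0.0494; simulation gives 0.0455, 0.0416 and 0.0352 at ρ = 0.5, 0.7 and 0.9. With a gate it is 0.025 in each case. Here the excess persists at high correlation.

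**5. The second Hochberg (4SC plus six functional endpoints).**
- *Global null, no gate:* it adds nothing. Suppose 4SC has p > 0.025 and an endpoint is rejected at rank i in this family. Removing 4SC moves that endpoint up one rank and adding VL MFF moves it down by at most one. Its rank in the key secondary family is therefore at most i, and it is rejected there too.
- *With a gate, if the second Hochberg is formal at 0.025 (an assumption):* let 4SC and five functional endpoints work, with one functional endpoint and VL MFF null. At ρ = 0 the null functional endpoint is falsely claimed at 0.025 through the second family and VL MFF at 0.0125 through the first: 1 − 0.975 × 0.9875 = 0.0372. Simulation gives 0.0347, 0.0322 and 0.0279 at ρ = 0.5, 0.7 and 0.9. With the gate but without the second Hochberg, the error is 0.021 to 0.025. So the gate alone is not enough if the second procedure is read as formal.

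**6. Rank-based intervals.** Suppose all seven one-sided p-values lie between 0.01 and 0.025. Hochberg declares all seven significant at the first step. The smallest p-value has rank 7, and its interval excludes the null only if p ≤ 0.025/7 = 0.0036, so the interval includes the null for an endpoint flagged significant. With assumed power of 50% to 90% per endpoint, at least one such contradiction occurs in 2% to 7% of simulated trials for ρ from 0 to 0.7, and in 7% to 10% at ρ = 0.9.

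**The case against.** The strongest reply is that a hierarchy is implied. There is one primary endpoint, Protocol 4.2.3 presents the key secondaries as corroborating it, and secondaries after a failed primary are customarily read as nominal. SAP 4.4.5 claims control only across the key secondaries, and it delivers that.

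The last part is true, but the implied gate does not fit the text. SAP 4.4.4.3 makes the tipping-point analysis conditional on a significant primary result, so the authors write that condition when they mean it. SAP 4.4.7.2 plans for a significant VL MFF result whether or not 4SC is significant.

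Two points on size stand. Zero correlation is an upper end, not a likely case: Protocol 4.2.3 reports that fat fraction tracks function, and both NSAA endpoints come from the same 17 items. And 0.025 of the total is the 4SC test's own allowance, so under the global null the part a gate removes is 0.0086 at ρ = 0.7 and 0.0016 at 0.9. It is larger in the partial null of step 4.

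It is also fair that the clauses in 4.4.2 and 4.4.5 covering all other analyses suggest the second Hochberg is supportive. The benefit wording attached to it points the other way, so its status needs stating. The interval point concerns presentation only.

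**Conclusion.** The concern holds. SAP 4.4.2 and 4.4.5 together allow a formal secondary claim after 4SC fails. The one-sided chance of at least one false formal claim under the global null is about 0.027 to 0.049 for a common correlation from 0.9 down to 0, and about 0.035 to 0.049 if the functional endpoints work but 4SC and VL MFF do not. These ranges rest on assumed equal correlations and normal test statistics. That there is an excess over 0.025 needs only that the endpoints are not perfectly correlated. The primary test is sound and its conclusion is unchanged. The SAP should be corrected because the gap affects how secondary results may be described.

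**What to change.** Three changes, all to SAP wording:

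- In 4.4.5 add: *The key secondary Hochberg family is tested only if 4SC is significant at one-sided 0.025; otherwise all key secondary p-values are nominal.* Align 4.4.7.2 with this.
- In 4.4.2 label the combined primary-plus-functional Hochberg as supportive, with no formal claim resting on it.
- In the overall summary table replace the rank-based intervals with Hochberg-adjusted p-values, and show 95% intervals labelled unadjusted, which 4.4.2 already provides in the individual tables. Read significance from the adjusted p-values only.

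The cost of the gate is that no formal secondary claim is possible if 4SC misses.

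The alternative is a single Hochberg over all eight endpoints at 0.025. Its global-null error is about 0.025 at ρ = 0 and 0.010 at ρ = 0.9, and it suits the view that 4SC and the functional endpoints matter equally. But it changes the 4SC test: with 90% power for 4SC alone, power falls to about 69% if no other endpoint works, and to about 82% to 85% if all eight have 90% power. The gate leaves the 4SC test as planned.

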4.4.6 Examination of Subgroups

Summaries, plots or analyses of efficacy or safety data presented by subgroup will only be produced in each case if there are at least 5 subjects per treatment arm in at least 2 of the respective subgroup levels.

4.4.6.1 Presentation of Efficacy Data by Subgroup

All repeat summaries and analyses of efficacy data by subgroups will be performed on the target population only and will be considered supportive and not subject to alpha control. Therefore, only nominal p-values will be presented.

In order to determine whether dose interruptions, modifications or starting dose have an impact on the efficacy of givinostat, the following subgroups of subjects will be defined:

- Subjects who maintained treatment for greater than 80% of the time versus those who did not. This will be equivalent to total percent compliance calculated as described in Section 3.4.
- Subjects whose total weight adjusted exposure (mg/kg) was $<$ versus \geq the median total weight adjusted exposure (mg/kg). For each subject the total weight adjusted exposure (mg/kg) will be calculated as:

$$\sum (\text{duration of dosing period (days)} * \text{total daily dose for dosing period (mg per kg)})$$

The median total weight adjusted exposure (mg/kg) will be calculated and used to determine the subgroups.

- Subjects who started on the higher dose specified in Protocol Versions ≤ 4.0 versus those who started on the lower dose specified in Protocol Versions > 4.0 .

The following endpoints will be summarised, plotted and analysed in the same way as described in Sections 4.1, 4.2, 4.3 and 4.4.2 for these subgroups:

- Change from baseline to 18 months of treatment with givinostat or placebo in 4SC
- Change from baseline to 18 months of treatment with givinostat or placebo in MRS VL MFF
- Change from baseline to 18 months of treatment with givinostat or placebo in time to rise from the floor
- Change from baseline to 18 months of treatment with givinostat or placebo in 6MWT
- Change from baseline to 18 months of treatment with givinostat or placebo in muscle strength evaluated by knee extension and elbow flexion

- Change from baseline to 18 months of treatment with givinostat or placebo in NSAA score
- Time to persistent loss of standing
- Proportion of subjects who lose ambulation

In order to determine whether the effects of givinostat versus placebo are related to the type of DMD mutation or the LTBP4 and SPP1 genotypes, three further subgroups of subjects will be defined: DMD mutation (Deletion, Duplication, Point Mutation), LTBP4 (IAMM, VTTT, Other) and SPP1 (TT, GT, GG). The following endpoints will be summarised and plotted for these three subgroups in the same way as described in Sections 4.1 and 4.2:

- Change from baseline to 18 months of treatment with givinostat or placebo in 4SC
- Change from baseline to 18 months of treatment with givinostat or placebo in MRS VL MFF
- Change from baseline to 18 months of treatment with givinostat or placebo in time to rise from the floor
- Change from baseline to 18 months of treatment with givinostat or placebo in 6MWT
- Change from baseline to 18 months of treatment with givinostat or placebo in muscle strength evaluated by knee extension and elbow flexion
- Change from baseline to 18 months of treatment with givinostat or placebo in NSAA score

In addition, the following endpoints will be summarised and analysed for the DMD mutation, LTPB4 and SPP1 subgroups in the same way as described in Sections 4.3.7, 4.3.8 and 4.4.2):

- Time to persistent loss of standing
- Proportion of subjects who lose ambulation

Finally, the following endpoints will be summarised, plotted and analysed as described in Sections 4.1, 4.2, 4.3 and 4.4.2 by baseline age category based on the re-derived age at first dose in years and months (6 – 7 years versus > 7 years). Note that subjects will be assigned to these subgroups so that any age from 6 to 7.9999 years is assigned to the 6-7 years group, any ages from 8 years onwards are assigned to the > 7 years group:

- Change from baseline to 18 months of treatment with givinostat or placebo in 4SC
- Change from baseline to 18 months of treatment with givinostat or placebo in time to rise from the floor
- Change from baseline to 18 months of treatment with givinostat or placebo in 6MWT
- Change from baseline to 18 months of treatment with givinostat or placebo in muscle strength evaluated by knee extension and elbow flexion

- Change from baseline to 18 months of treatment with givinostat or placebo in NSAA score
- Percent predicted 6MWT
- Time to 10% persistent worsening in 6MWT
- Proportion of subjects with $\geq 10\%$ persistent worsening in 6MWT
- Time to persistent loss of standing
- Proportion of subjects who lose ambulation

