3.4 Administration of Investigational Medicinal Products

The duration (days) of exposure to the study treatment will be calculated as date of last exposure to study drug – date of first dose + 1. Where these data are analysed

prior to study completion, the duration of exposure will be calculated as follows for subjects who have not yet completed the study: date of data cut for analysis – date of first dose + 1. The actual duration of treatment will be calculated as the exposure period – number of days on which treatment was temporarily withdrawn (calculated from the start and end dates of any modification recorded as ‘Dose temporarily stopped’ or ‘Dose skipped’). Where only the morning or evening dose is recorded as skipped, this will be counted as 0.5 days of withdrawn treatment.

At each visit, the ‘Subject Compliance’ page of the eCRF will be completed with details of the last IMP dose taken, any doses missed and the date and timing of the first IMP dose at the visit. For subjects who were enrolled after the introduction of this eCRF page, total percent compliance for the study will be calculated as follows:

Total number of expected doses = Duration of exposure (days) x 2

Total number of missed doses = Sum of number of missed doses at all visits

Total number of doses taken = Total expected doses – Total missed doses

Total percent compliance = Total doses taken / Total expected doses x 100

For subjects who were enrolled prior to the introduction of the ‘Subject Compliance’ eCRF page, total percent compliance will be calculated using the information collected on the ‘Investigational Medicinal Product Administration’ page as follows:

Total number of expected doses = Duration of exposure (days) x 2

Total number of missed doses = Number of days on which treatment was temporarily withdrawn or skipped x 2*

Total number of doses taken = Total expected doses – Total missed doses

Total percent compliance = Total doses taken / Total expected doses x 100

* Number of days on which treatment was temporarily withdrawn will be calculated from the start and end dates of any modification recorded as ‘Dose temporarily stopped’ or ‘Dose skipped’. Where only the morning or evening dose is recorded as skipped, this will be counted as 0.5 days of withdrawn treatment equating to one dose missed for the respective day.

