Subjects will be categorised as ‘compliant’ or ‘not compliant’, where compliant subjects are those who achieve >80% overall compliance according to the above calculation.

A table will be presented to summarise the duration of exposure to study treatment, actual duration, percent compliance and number and percentage of subjects categorised as compliant, by treatment group and overall for the safety analysis set. This table will also summarise the total daily dose of treatment administered by visit, allowing for any dose modifications. This will be presented both for total daily dose measured in mg, as well as for total daily dose measured in mg per kg. Total daily dose (mg per kg) will be calculated as: total daily dose (mg) at the time of the visit / most recent non-missing subject weight (kg) at the time of the visit. In addition, the table will summarise total weight adjusted exposure (mg/kg), calculated as:

$$\sum (\text{duration of dosing period (days)} * \text{total daily dose for dosing period (mg per kg)})$$

where the duration of dosing period refers to the duration each different dose was taken, excluding interruptions and skipped doses.

Details about medication bottles dispensed and returned, study drug administration and modifications, compliance and derived variables will be listed for the safety analysis set.

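### The subgroup for treatment maintained more than 80% of the time uses a compliance figure that ends at the last dose, so boys who stop early for good can be classed as having maintained treatment

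*SAP*

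**What the plan says.** SAP 4.4.6.1 gives the purpose of three dosing subgroups: "In order to determine whether dose interruptions, modifications or starting dose have an impact on the efficacy of givinostat". The first is "Subjects who maintained treatment for greater than 80% of the time versus those who did not". The SAP then fixes how it is computed: "This will be equivalent to total percent compliance calculated as described in Section 3.4".

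SAP 3.4 builds that percentage in steps:

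- Duration of exposure is "calculated as date of last exposure to study drug – date of first dose + 1". For analyses run before the study is complete, boys still in the study get a different end point: "date of data cut for analysis – date of first dose + 1".
- The denominator is the same for all boys: "Total number of expected doses = Duration of exposure (days) x 2".
- For boys enrolled after the Subject Compliance eCRF page came in, the count is "Total number of missed doses = Sum of number of missed doses at all visits". For boys enrolled before it, missed doses come from the drug administration page and consist of temporary stops and skipped doses.
- The cut-off is that "compliant subjects are those who achieve >80% overall compliance according to the above calculation".

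SAP 3.5 lists a permanent stop as a type of dose modification separate from a temporary stop or a skipped dose. No rule in SAP 3.4 or 4.4.6.1 adds doses to the denominator, or to the missed count, after a permanent stop.

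**The concern.** The label describes the share of time a boy was on treatment. The formula measures how well he took the drug while he was still taking it. The two agree for a boy who completes 18 months and part company for a boy who stops for good.

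A boy with very little drug can therefore sit in the group meant to show sustained treatment, while a completer with long temporary stops sits in the other. A reader of the output would take the label literally. The split is applied to 4SC, VL MFF, rise from floor, 6MWT, muscle strength, NSAA score, loss of standing and loss of ambulation. SAP 4.4.6 requires at least 5 boys per arm in at least two levels. With only two levels, both must qualify, so moving a few boys may change the make-up of a small lower group or decide whether the analysis is produced at all.

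A second, smaller problem is that missed doses come from different eCRF pages for earlier and later enrollees. For later enrollees the SAP does not say whether doses withheld during a temporary stop are entered as missed.

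**Working it through.** The documents state no figure for this subgroup, so there is none to reproduce. The check applies the SAP 3.4 rule to simple cases.

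**Inputs**

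- Planned treatment: end-of-study visit at Week 72 (Protocol 9.1.8). 72 × 7 = 504 days; 504 × 2 = 1008 doses.
- Exposure days *E*: last dose date − first dose date + 1 (SAP 3.4).
- Missed doses *M*: counted up to the last dose (SAP 3.4).
- Cut-off: above 80% (SAP 3.4 and 4.4.6.1).

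**Formulas**

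- SAP 3.4: 100 × (2*E* − *M*) / (2*E*)
- Share of the planned period: 100 × (2*E* − *M*) / 1008

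**Results**

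| Case | SAP 3.4 score | Class under SAP | Share of planned 1008 doses |
|---|---|---|---|
| Stops for good day 28, none missed | 56/56 = 100% | maintained | 56/1008 = 5.6% |
| Day 84, none missed | 168/168 = 100% | maintained | 16.7% |
| Day 84, about 10% missed (17 doses) | 151/168 = 89.9% | maintained | 15.0% |
| Day 84, 25% missed (42 doses) | 126/168 = 75.0% | not maintained | 12.5% |
| Day 90, none missed | 180/180 = 100% | maintained | 180/1008 = 17.9% |
| Day 252, none missed | 100% | maintained | 50.0% |
| Day 336, none missed | 100% | maintained | 66.7% |
| Completes day 504, 110 days of temporary stops | (1008 − 220)/1008 = 78.2% | not maintained | 78.2% |

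The day-90 boy and the last boy come out in the wrong order: 90 days on drug is classed as maintained, and 504 − 110 = 394 days is not. The 78.2% is secure only for earlier enrollees, because for later ones it depends on temporary stops being entered as missed doses.

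**Limits of the misclassification.** With full dosing, 404 days already exceed 80% of 504 (403/504 = 79.96%; 404/504 = 80.2%), so stopping at day 404 or later with no missed doses is classed correctly. A boy who took 80% or less of his doses before stopping is also classed correctly. The choice of period barely matters: with 18 months taken as 548 days, the day-90 boy is at 90/548 = 16.4%.

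**Do these boys enter the analysis?** Yes. The ITT set (SAP 3.1.1) keeps dosed boys who have a qualifying post-baseline 4SC record, whether or not they discontinue. SAP 4.4.4.1 imputes scheduled visits after withdrawal. VL MFF is a partial exception, because the MR cohort needs at least one post-baseline MR assessment and an early stopper may have none.

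**Does another rule repair it?** No. The data-cut end point applies only to analyses before study completion. For earlier enrollees, a permanent stop is neither a temporary stop nor a skipped dose. For later enrollees, no rule adds doses after the stop.

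**The case against.** The strongest reply is that little depends on this. SAP 4.4.6.1 makes the subgroup analyses supportive, with nominal p-values. The 80% rule is defined openly and cross-referenced. The companion subgroup on total weight-adjusted exposure sums days times dose, so it does fall when a boy stops early, and SAP 3.4 and 3.5 tabulate actual duration and permanent stops. All of this is correct and limits the importance of the point. It does not make the label true, and the companion subgroup mixes time on drug with dose level, so it does not isolate what the first subgroup claims to measure.

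A reader might infer four stronger things that the documents do not support:

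- **That early stoppers dilute the effect in the maintained group, or hide the cost of losing treatment.** Their missing 18-month values are Class 1 unless the last assessment before withdrawal was missing through physical inability (SAP 4.4.4.1). Class 1 values of the continuous measures take the mean of the boy's own arm, steroid stratum and Group; NSAA items use the corresponding mode. An early givinostat stopper would usually carry a typical givinostat value. Neither the size nor the direction of any distortion can be stated, and there is generally no observed off-drug 18-month outcome to hide.
- **That membership follows starting dose through the two eCRF pages.** Nothing in the documents dates the Subject Compliance page relative to the dose change.
- **That about 9 of 110 boys are misplaced.** 8% × 110 = 8.8 comes from a planning allowance for drop-out. It is not a count of early permanent stops, and some of those boys would be classed correctly.
- **That long temporary stops commonly push completers below 80%.** Protocol 4.2.2 reports platelet falls resolving within 2 to 3 weeks of stopping drug. At three weeks each, 110 days means more than five such stops, and no document suggests that is frequent.

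**Conclusion.** The point holds as an error of definition. Followed as written, SAP 4.4.6.1 classes a boy who stops early for good as having maintained treatment, provided he took more than 80% of his doses up to that stop. At day 90 the gap is 100% by the formula against 17.9% of the planned period.

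The consequence is misclassification in a supportive subgroup analysis: the maintained group can contain boys with little drug and mostly imputed 18-month outcomes. The number affected is not given and the direction of any effect on the estimates is uncertain. The primary analysis, the key secondary tests and alpha are not affected. The difference in how missed doses are counted is a further inconsistency of unknown size.

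The figures assume a 504-day planned period and, except where stated, no missed doses before the stop. The correction is worth making because it is cheap and the output would otherwise be read at face value.

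**What to change.** In SAP 4.4.6.1, define the subgroup as days on drug (or doses taken) divided by each boy's planned treatment period:

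- for completers, from first dose to the actual 18-month visit;
- for boys who stop permanently, from first dose to planned Week 72, with time after the stop counted as off treatment;
- with the result capped at 100%.

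A flat 1008-dose denominator would not do. Visits can fall 7 days either side of Week 72, and SAP 2.9 recognises a 60-day extended window. A fully adherent completer would score 444/504 = 88.1% at day 444 and 564/504 = 111.9% at day 564.

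State in SAP 3.4 that temporary stops count as missed doses under both versions of the eCRF, and keep the per-visit missed-dose counts where they exist. Keep the SAP 3.4 percentage, labelled as compliance while on treatment.

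The cost is a wording change and a small programming change using dates already collected. Fewer boys will be classed as having maintained treatment, and the lower group will include boys with imputed outcomes. A footnote should say so, because the lower group will then not be direct evidence of what happens after stopping.
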